8.7.6 Sputum for microbiology culture

If sputum for microbiology culture is collected for clinical purposes, the results from sputum culture (qualitative and quantitative) will be listed.

8.7.7 Other safety assessments

Gynaecological assessment (including assessment of inflammation of cervix and vagina), acute COPD exacerbation assessment, additional investigations for COPD exacerbation, additional investigations for pneumonia and dermatologic assessment data will be listed.

8.8 Other analysis

8.8.1 Efficacy analyses based on acute exacerbations of COPD adjudication

An independent, external IAC has been set-up to carry out responsibilities as detailed in the Independent Adjudication Committee Charter, Final Version 1.0, dated 07 February 2017.

Specific details regarding procedures for clinical adjudication of the components of the endpoint as well as the adjudication data collection/transfer process are fully described in the following documents:

- IAC Charter
- Systems Requirements Specifications, Final Version 2.0, dated 28 February 2017
- Data Delivery Specification, Final Version 1.0, dated 10 May 2017.

Once subjects have completed study treatment, the events to be adjudicated by the IAC are all new reports of acute exacerbation of COPD and events of hospitalisation due to new exacerbations of COPD (dataset AECOPD – AECOPD Adjudication Assessment). Each Adjudication case will be reviewed independently by each of the three adjudicators. If the adjudicators agree on all non-text fields the case will be complete and final. If they do not agree, they will meet and complete in Consensus.

The data derivations and statistical analyses to be performed based on acute exacerbations of COPD adjudication are described below:

- Number and percentage of patients with positively adjudicated moderate/severe COPD exacerbations will be provided by treatment regimen
- Number of positively adjudicated moderate/severe COPD exacerbations during the study will be provided by treatment regimen
- Rate of positively adjudicated moderate/severe COPD exacerbations per patient per year will be provided for each treatment regimen (same approach as for the non-adjudicated data)
- The proportion of patients with positively adjudicated moderate/severe COPD exacerbations during the study will be compared between treatment regimens using Pearson's Chi-square test (or Fisher's exact test as appropriate) (two-sided test at 5% alpha level)
- The time to next positively adjudicated moderate/severe COPD exacerbation will be analysed using the Kaplan-Meier method. Patients without a positively adjudicated moderate/severe COPD exacerbation or who are discontinued before having it will be

considered as “censored” patients. The same approach as for the non-adjudicated data will be used.

- Similar analyses as above will be performed for positively adjudicated moderate COPD exacerbations and for positively adjudicated severe COPD exacerbations separately.

8.8.2 PK/PD analyses

Subjects [REDACTED]

[REDACTED] sample to be taken

taken 4-8 hours post-dose, and one sample no earlier than 12 hours post-dose.

This plan does not address the PK/PD analyses of BCT197 (nonlinear mixed effects PK/PD modelling evaluating the relationship between BCT197 exposure and efficacy/safety endpoints) for this study. These analyses will be performed by ICON Pharmacokinetics, Pharmacodynamics, Modelling and Simulation Department and will be detailed in a separate analysis plan. Results from the PK/PD modelling will be reported separately from the CSR. An overview of the PK/PD analyses of BCT197 is provided here: “A population PK model for BCT197 will be developed using nonlinear mixed effects and the sparsely sampled PK concentration, from which measures of BCT197 exposure will be derived. If necessary, additional PK data from more intensively sampled studies will be included to support the development of the structural model. The population PK model will also evaluate the potential influence of demographic factors and covariates on the PK of BCT197. A graphical exploration will be undertaken to identify potential relationships between BCT197 exposure and selected efficacy/safety endpoints to be formally evaluated using nonlinear mixed effects modelling (including BCT197 exposure/QTc modelling)”.

BCT197 concentrations will be summarised on the PK population by descriptive statistics stratified by BCT197 dose-level and time-point, and including the geometric mean and coefficient of variation.

A graphical representation of the BCT197 concentrations distribution using mean plots (mean and SD) will be provided over time per BCT197 dose-level on the PK population. Both dose-levels will be plotted on the same graph.

8.8.3 Subgroup analysis

To verify the internal consistency of the trial data and results, statistical analyses of the primary efficacy endpoint, i.e. summarisation of FEV1 results (absolute values and changes from baseline) by treatment regimen and visit (until Day 7) on the ITT population, will be repeated for the following subgroups of patients:

- Severity of COPD disease at screening (Gold C, Gold D)
- Sex (Males, Females)
- Geographic region (Europe, Rest of World)
- Blood eosinophils relative count (%) at baseline ($< 2\%$, $\geq 2\%$)

- FEV1 % of predicted normal value post-bronchodilator at baseline (based on tertiles)
- FEV1 absolute value post-bronchodilator at baseline (based on tertiles)
- FEV1/FVC % of predicted normal value post-bronchodilator at baseline (based on tertiles)
- FEV1/FVC absolute value post-bronchodilator at baseline (based on tertiles)
- COPD exacerbation aetiology (primary reason) at screening (Infection, Environmental Pollutants, Extrapulmonary Co-morbidities, Concomitant Pulmonary Co-morbidities, Allergic, Other)
- Change in sputum production at screening (No Change, Yes: Purulent; Yes: Non Purulent)
- Cardiovascular comorbidities at screening (Presence, Absence)
- Time from start of current COPD exacerbation to first IMP dosing (≤ 2 days, 3-4 days or ≥ 5 days)
- Protocol Version under which the patient was enrolled to (Protocols V2.0 and V3.0, Protocols V4.0 and V5.0).

For each subgroup of patients, the mean change in FEV1 from baseline (pre-dose) to Day 7 will be compared between treatment regimens using a one-way ANOVA test, and the associated two-sided p-value will be reported in the summary table and regarded as descriptive.

Should the normality assumptions for change in FEV1 from baseline (pre-dose) to Day 7 not be met (the skewness and kurtosis measurements will be considered as supportive indicators), the relationship between change in FEV1 from baseline (pre-dose) to Day 7 and treatment regimen will be tested using the non-parametric approach of Kruskal-Wallis test (or Wilcoxon Rank-Sum test for pairwise treatment regimens).

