13.5 Description of Statistical Analyses

13.5.1 General Considerations

The statistical evaluation will be performed by ICON using SAS®, Version 9.3 or later. Data will be analysed by either enumeration of subjects displaying distinctive characteristics within each treatment regimen or by descriptive statistical summaries such as means, SD, medians, and ranges for continuous measures. Categorical variables will be presented by the number of observations and absolute and relative (%) frequency.

For efficacy data, summary statistics (N, mean, SD, median minimum and maximum for continuous data, and N [%] for categorical data) will be presented at each visit.

Similarly, changes from Baseline (or percentage change from Baseline if appropriate) will be summarised in a similar manner.

The main population for efficacy analysis will be the ITT population.

Unless stated otherwise, the Baseline value for a variable will be the latest value taken prior to the first dose of study medication.

Data in summary tables will generally be presented on an Observed Cases basis.

Unless stated otherwise, all statistical tests will be two-sided and conducted at the 5% level, and all quoted confidence intervals will be two-sided 95% confidence intervals. All three treatment regimens will be assessed by pairwise comparisons, no adjustment for multiplicity will be made and all analyses will be considered as exploratory analyses.

Full details of the statistical analysis will be given in the SAP.

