8.1.4 Statistical significance

Unless otherwise stated, all statistical testing will be two-sided and conducted at the significance (alpha) level of 0.05. Two-sided 95% confidence intervals (CIs) will be provided when relevant. All three treatment regimens will be assessed by pairwise comparisons for efficacy data, and no adjustment for multiplicity will be made.

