8.6.1.2 Treatment by center interaction analysis (multi-center study)

No analysis will be made to assess the treatment-by-center interaction.

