8.6.2.1 Primary analysis

The primary analysis of efficacy will be based on the ITT population and observed cases.

The primary analysis will compare each of the treatment regimens together using pairwise comparison tests based on a mixed model for repeated measurements (MMRM) using an unstructured covariance matrix and the Kenward-Roger adjustment for the denominator degrees of freedom. The model will use FEV1 absolute changes at Days 2, 3, 4, 5, 6 and 7, and will include treatment [REDACTED] severity of airflow limitation at baseline (post-bronchodilator FEV1 at baseline (pre-dose) <30% or ≥30% of predicted normal value), blood eosinophils (%) value at baseline (<2% or ≥2%), time from start of current COPD exacerbation to first IMP dosing (≤2 days, 3-4 days or ≥5 days), presence of cardiovascular comorbidities at screening (yes, no) and COPD exacerbation treatment at screening (systemic corticosteroids only, antibiotics only or both systemic corticosteroids and antibiotics) as fixed effects and baseline FEV1 value as covariate. In addition the baseline FEV1 value-by-visit and the treatment-by-visit interactions will be included in the model.

LSMEAN and standard error (SE) of each treatment regimen as well as the adjusted mean difference between treatment regimens and associated two-sided 95% CIs will be obtained from the MMRM model at Days 2, 3, 4, 5, 6 and 7. Each pairwise treatment regimen comparison will be tested at an alpha level of 5%. Difference will be considered and confirmed between pairwise treatments if the two-sided P-value for the test for difference is below 0.05. P-values of the effects will also be presented.

Hypotheses:

The 'superiority' null hypothesis will be:

$H_0: T2-T1 = 0$ (T2 is equivalent to T1) vs the alternative

$H_a: T2-T1 \neq 0$ (T2 is different to T1)

MMRM model and SAS code:

The SAS code used to implement linear mixed model for repeated measures for FEV1 and 95% CIs of differences between treatments will be similar to that shown below:

PROC MIXED data = dataset;

CLASS ID trt visit severity eosino time_symp cv_comorb COPD_trt;

*MODEL change = trt visit trt*visit severity eosino time_symp cv_comorb COPD_trt baseline*

*baseline*visit / ddfm=KenwardRoger;*

REPEATED visit / subject=ID type=UN;

*LSMEANS trt*visit / cl;*

LSMEANS trt / cl;

*LSMESTIMATE trt*visit*

'A vs B: Visit 2' 1 0 0 0 0 0 -1 0 0 0 0 0 0 0 0 0 0 0,

'A vs B: Visit 3' 0 1 0 0 0 0 0 -1 0 0 0 0 0 0 0 0 0 0,

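### SAP 8.8.3 sets out to verify consistency across subgroups but plans only tests within each level, and none of whether the effect differs between levels

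*SAP*

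**What the plan says.** SAP 8.8.3 gives its purpose as "To verify the internal consistency of the trial data and results". It repeats the FEV1 summaries to Day 7 in the ITT population for 13 factors: GOLD category, sex, region, eosinophils, four baseline spirometry measures cut at tertiles, exacerbation aetiology, sputum change, cardiovascular comorbidity, time from onset to dosing, and protocol version. In each level the mean Day 7 change "will be compared between treatment regimens using a one-way ANOVA test". Kruskal-Wallis (Wilcoxon for pairs) replaces it if normality looks doubtful. On status, "the associated two-sided p-value will be reported in the summary table and regarded as descriptive".

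SAP 8.1.4 states that "no adjustment for multiplicity will be made". Protocol 13.5.1 goes further: "no adjustment for multiplicity will be made and all analyses will be considered as exploratory analyses".

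No treatment-by-subgroup term appears anywhere. The only interactions in the primary model are these: "In addition the baseline FEV1 value-by-visit and the treatment-by-visit interactions will be included in the model". For centres, SAP 8.6.1.2 says: "No analysis will be made to assess the treatment-by-center interaction".

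**The concern.** Consistency is a question about differences between levels: is the effect in women like that in men, or the effect at high eosinophils like that at low? An ANOVA inside one level asks something else, namely whether the three arms differ there. Whether it reaches 5% depends heavily on how many patients the level holds. Significance in one level and not in its neighbour is thus weak evidence of a differing effect, and non-significance in both is weak evidence of agreement.

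The ANOVA also departs from the primary analysis in three ways:

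- It drops baseline FEV1 and the five other covariates in SAP 8.6.2.1.
- It uses only patients with an observed Day 7 value, so the missing-at-random argument made for the MMRM in SAP 7.2.1 does not carry over.
- As an omnibus three-arm test, it gives no adjusted difference from placebo with a confidence interval.

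At stake is how subgroup results are read in a study that SAP section 6 calls proof-of-concept and hypothesis-generating.

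**Working it through.** **Inputs.** From SAP section 5: difference 100 mL, SD 230 mL, two-sided 5%, 80% power, 85 evaluable per arm. Allocation is 1:1:1 (SAP 3.2.1). The SAP calls 230 mL the SD of the difference; protocol 13.1 says only standard deviation. It is taken here as the per-arm SD of the change, which reproduces the stated sample size.

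**The plan's own figure.** n per arm = 2 × (1.96 + 0.8416)² × 230² / 100² = 83.04, rounded up to 84. The t-based value is 84.01, rounded up to 85, as stated. Power at 85 per arm is 80.9% (normal) or 80.5% (t). The SAP gives no error rate or power for the subgroup tests.

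**Count of levels.** Five two-level factors before and after the spirometry items (GOLD, sex, region, eosinophils, cardiovascular comorbidity) give 10, and protocol version adds 2. Four tertile factors give 12. Aetiology gives 6, sputum 3 and time to dosing 3. Total: 10 + 2 + 12 + 6 + 3 + 3 = 36.

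**Identical effect everywhere.** Let both regimens be 100 mL better than placebo in every level. The arm means are 0, 100 and 100, with average 66.7, so the squared deviations sum to 6,667. The noncentrality is λ = n × 6,667 / 230², with 2 and 3n − 3 degrees of freedom.

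| Level size | n per arm | λ | ANOVA power |
|---|---|---|---|
| Whole trial | 85 | 10.7 | 84% |
| Half | 42.5 | 5.4 | 52% |
| Tertile | 28.3 | 3.6 | 36% |
| One sixth | 14.2 | 1.8 | 19% |

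For a 50/50 factor and one regimen against placebo, the SE in each half is 230 × √(2/42.5) = 49.9 mL and power is 51.8%. Both halves are significant with probability 0.518² = 27%. Exactly one is significant with probability 2 × 0.518 × 0.482 = 50%.

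A simulation of 2,000 trials used 13 overlapping factors. Level sizes were assumed: two-level factors at 50/50 except protocol version at 20/80, three-level factors in thirds, aetiology at 50% plus five levels of 10%. With the uniform effect, about 8 of 13 factors showed a mix of p < 0.05 and p ≥ 0.05.

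**No effect anywhere.** Expected nominal positives are 36 × 0.05 = 1.8 if every level is testable. The chance of at least one is 1 − 0.95³⁶ = 84% under independence. The same patients recur in every factor, so independence fails; the simulation gives about 67%.

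**Interaction tests instead.** Thirteen tests give 13 × 0.05 = 0.65 expected false positives and 1 − 0.95¹³ = 49% for at least one if independent (48% simulated). With the uniform 100 mL effect they flag about 0.64 of 13 factors, against 8 with mixed within-level results. Their power is low. For a 50/50 factor the SE of the difference in effects is 230 × √(4/42.5) = 70.6 mL, so power is about 29% for a 100 mL difference in effect and 81% for 200 mL.

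**The case against.** The best defence is that this is a descriptive table in a study declared exploratory. SAP 8.8.3 labels the p-values descriptive and attaches no threshold, decision rule or claim to them. The tables also show n, mean and SD by regimen and visit, so a crude difference from placebo can be read for each level. For protocol version, SAP 8.6.2.3 already plans an adjusted MMRM in patients enrolled under V4.0 and V5.0. Interaction tests are weak and carry their own false-positive rate.

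Much of this stands, and it rules out several stronger readings that a reader might infer:

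- That the SAP will declare consistency or inconsistency from these p-values. It contains no such rule.
- That missing multiplicity adjustment is itself the defect. For descriptive p-values in an exploratory study it is a declared choice.
- That false signals are certain, or that 84% is the realistic figure. They are likely, and 84% needs independence.
- That the ANOVA is confined to study completers. It needs a baseline and a Day 7 value; later withdrawals are included, and planned dropout is only about 5%.
- That some aetiology levels will be nearly empty. This is plausible, but neither document gives frequencies.

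What the defence does not meet is the mismatch between aim and method. Calling a p-value descriptive does not make it describe the difference between levels. The SAP is also uneven here: 8.6.4.6 declines any test of BODE in patients enrolled under V2.0 and V3.0 because they are few, while 8.8.3 schedules an ANOVA in that same group.

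**Conclusion.** The point holds as a mismatch between the stated purpose of SAP 8.8.3 and its only test. Under a perfectly uniform 100 mL effect of both regimens, power falls from 84% overall to between 52% and 19% in levels of a half to a sixth of the trial. Apparent disagreement between levels is then the expected pattern. Spurious inconsistency from low within-level power matters more than multiplicity.

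The power figures rest on the SAP's 100 mL and 230 mL, 85 evaluable per arm, the same SD in every level, and reading each p-value against 5%. The 67% and the 8 of 13 also rest on assumed level sizes. The primary result is untouched, so this is a worthwhile, inexpensive improvement to a descriptive secondary analysis.

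**What to change.** Replace the within-level p-values in SAP 8.8.3 as follows:

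- Fit the primary MMRM with treatment-by-subgroup and treatment-by-subgroup-by-visit terms, one factor at a time. If it does not converge, use a Day 7 ANCOVA with a treatment-by-subgroup term.
- Report the Day 7 difference of each regimen from placebo with a 95% CI for every level, in a forest plot.
- Give one interaction p-value per factor, labelled descriptive.
- State in advance how sparse levels will be pooled, or that they will only be summarised.
- For factors derived from baseline FEV1, omit the overlapping airflow-severity term.
- State that a non-significant interaction does not prove consistency and that interpretation rests on the intervals.

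The cost is SAP wording and 13 model runs in place of 36 tests. Eosinophils, cardiovascular comorbidity and time to dosing are already in the model as main effects. Aetiology is the hardest case: 3 arms × 6 levels × 6 visits gives 108 cells under an unstructured covariance, hence the ANCOVA fallback and the sparse-level rule. The limits remain about 29% power for a 100 mL difference in effect in a 50/50 factor, and about a 49% chance of at least one false positive over 13 tests if independent.

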8.9 Interim analysis

No formal interim analysis is planned for this study.

However, an independent, external DMC has been set-up to carry out responsibilities as detailed in the Data Monitoring Committee Charter, Final Version 1.0, dated 01 February 2016.

Accumulating unblinded safety data of BCT197 were reviewed periodically (approximately quarterly) by the DMC. Should safety concerns be identified, a decision might be taken to halt the trial.

A separate DMC SAP, Final Version 2.0, dated 13 December 2016, has been developed to describe the data derivations and data summaries to be presented for the DMC analysis of Clinical Protocol MBCT206, for comparing the safety of two different dosing regimens of BCT197 when added to SoC versus placebo added to SoC for the treatment of acute respiratory exacerbations of COPD requiring hospitalisation in adults.

9 CHANGES TO PLANNED ANALYSIS FROM STUDY PROTOCOL

- **Definition of PP population:**
The PP definition stated in the protocol was clarified, in that only key inclusion/exclusion criteria with respect to factors likely to affect the assessment of efficacy need to be satisfied to include a subject in the PP population.
- **PP analyses:**
A PP analysis was added for the secondary and exploratory efficacy endpoints for this PoC and hypothesis-generating study. This PP analysis was initially planned in the study protocol on the primary efficacy endpoint only.
- **Cumulative oral/IV steroid dose analysis:**
The exploratory endpoint specified in the study protocol is “Cumulative oral/IV steroid dose from Day 1 to Day 14 and from Day 14 to Week 26”. This analysis was finally performed during the duration of current COPD exacerbation (i.e. from the date when symptoms started until the date when symptoms stopped) upon Mereo’s request. Sponsor was more interested in the amount of systemic steroids needed to control the current COPD exacerbation.

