2.3 Exploratory objectives

Exploratory assessments will evaluate:

1. Exploratory composite scale endpoints comparing among the three groups at Weeks 8, 12 and 26:
 - Number of events of worsening of symptoms warranting the addition of antibiotics
 - Number of events of worsening of symptoms warranting an increase of oral dose of corticosteroids or initiation of new oral corticosteroids
 - Number of events of worsening of symptoms requiring additional treatment with oral corticosteroids and/or antibiotics after completion of the initial regimen
 - Number of events of COPD exacerbations that required re-hospitalisation
 - Number of COPD-related deaths
2. Chronic respiratory questionnaire (CRQ) at Baseline, Day 14 and at Weeks 8, 12 and 26 to evaluate recovery comparing among the three groups over time
3. Cumulative oral/IV steroid dose on Days 1 to 14, and from Day 14 to Week 26
4. Change in inflammatory blood biomarkers (IL-6, TNF- α , fibrinogen, high-sensitivity C-reactive protein [hs-CRP], and myeloperoxidase [MPO]) daily during Part 1 of the study, and at Weeks 8, 12 and 26
5. Explore the relationship between BCT197 exposure and efficacy/safety endpoints
6. Change from baseline in modified Medical Research Council (mMRC) dyspnoea scale over time
7. Body mass index, airflow Obstruction, Dyspnoea and Exercise (BODE) index among the three groups at Day 14.

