4.3 Exploratory endpoints

The exploratory endpoints of this study are:

1. Exploratory composite scale comparing the following among the three groups at Week 8, 12 and 26:
 - Number of events of worsening symptoms warranting the addition of antibiotics
 - Number of events of worsening symptoms warranting an increase in dose of oral

-
- corticosteroids or initiation of new oral corticosteroids
- Number of events of worsening symptoms requiring additional treatment of oral corticosteroids and/or antibiotics after completion of the initial regimen
 - Number of events of COPD exacerbation requiring re-hospitalisation
 - Number of COPD-related deaths.
2. Change in CRQ from baseline at Day 14 and Weeks 8, 12 and 26 to evaluate recovery, comparing among the three groups over time
 3. Cumulative oral/IV steroid dose from Day 1 to Day 14, and from Day 14 to Week 26
 4. Change in inflammatory blood biomarkers (IL-6, TNF- α , fibrinogen, hs-CRP, and MPO) daily during Part 1 of the study, and at Weeks 8, 12 and 26
 5. Relationship between BCT197 exposure and efficacy/safety endpoints
 6. Change from baseline in mMRC dyspnoea scale over time
 7. BODE index among the three groups at Day 14.

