7.1.4.16 Cumulative oral/IV steroid dose

The cumulative oral/IV steroid dose during the duration of current COPD exacerbation will be derived on a patient level from the 'Prior (Last 6 months medication) and Concomitant Medication' form of the eCRF. The medications recorded on this form to be considered for this exploratory endpoint will verify:

- Systemic corticosteroids: ATC code 'H02'
- Route 'IV = intravenous' or 'PO = oral'
- Medication administered for COPD exacerbations only (i.e. with indication = 'COPD exacerbation: current/during the study') and taken during the duration of current COPD exacerbation (i.e. from the date when symptoms started until the date when symptoms stopped).

Moreover, the dose of treatment recorded on the form for selected systemic corticosteroids will be converted to 'mg', in case the unit recorded on the form is not 'mg'.

Then a correction factor will apply on the oral/IV steroid dosages (mg) using dosing equivalencies, i.e.:

- 1 mg of betamethasone = +/- 7 mg of prednisone equivalence
- 1 mg of cortisone = +/- 0.2 mg of prednisone equivalence
- 1 mg of dexamethasone = +/- 7 mg of prednisone equivalence
- 1 mg of hydrocortisone = +/- 0.25 mg of prednisone equivalence
- 1 mg of methylprednisolone = +/- 1 mg of prednisone equivalence
- 1 mg of prednisolone = +/- 1 mg of prednisone equivalence
- 1 mg of triamcinolone = +/- 1 mg of prednisone equivalence.

Finally, the cumulative oral/IV steroid dose (prednisone equivalent dose) per patient will be calculated as the sum of all prednisone equivalent doses taken by the patient each day during the duration of current COPD exacerbation.

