8.6.4.3 Cumulative oral/IV steroid dose during the duration of current COPD exacerbation

A descriptive summary table will be presented by treatment regimen for the cumulative oral/IV steroid dose (prednisone equivalent dose) during the duration of current COPD exacerbation. The cumulative prednisone dose will be compared between treatment regimens using a one-way ANOVA test, and the associated two-sided p-value will be reported in the summary table.

Should the normality assumptions for cumulative prednisone dose not be met (the skewness and kurtosis measurements will be considered as supportive indicators), the relationship between cumulative prednisone dose and treatment regimen will be tested using the non-parametric approach of Kruskal-Wallis test (or Wilcoxon Rank-Sum test for pairwise treatment regimens).

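### The cumulative steroid dose is summed only until symptoms stop, so faster symptom relief can lower the total without any change in prescribing, and the listed fixed-window analyses are not done

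*SAP*

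**What the plan says.** Protocol 8.3, 11.2 and 13.4.3 define the endpoint over two fixed periods. The SAP repeats them as an objective in 2.3 ("Cumulative oral/IV steroid dose on Days 1 to 14, and from Day 14 to Week 26") and as an endpoint in 4.3 ("Cumulative oral/IV steroid dose from Day 1 to Day 14, and from Day 14 to Week 26").

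The derivation and the analysis use neither period. SAP 7.1.4.16 selects oral and IV systemic corticosteroids given for COPD exacerbations, converts them to prednisone equivalents, and sums those taken "from the date when symptoms started until the date when symptoms stopped". SAP 8.6.4.3 compares that total between regimens by one-way ANOVA without covariates, with a rank test as fallback.

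SAP 9 discloses the change ("This analysis was finally performed during the duration of current COPD exacerbation") and gives the reason: "Sponsor was more interested in the amount of systemic steroids needed to control the current COPD exacerbation". It does not keep the protocol analysis as a supportive table, and it gives no separate reason for dropping the period after Day 14.

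**The concern.** A cumulative dose is interpretable between arms when both arms are counted over the same time. Here the counting period has a different length for each patient, and its end is an outcome of the exacerbation under treatment. Protocol 9.2 states that BCT197 is intended to speed recovery. If it brings the symptom stop date forward, the period shortens, and any steroid still being taken after that date leaves the total. The comparison could then suggest steroid sparing when prescribing was the same in every arm.

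There are three smaller problems:

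- The period opens before the first study dose, so some steroid that the drug could not have affected is counted.
- It has no end for a patient whose symptoms never stop, or who dies or withdraws with symptoms ongoing.
- Nothing in the SAP measures cumulative dose from Day 14 to Week 26, although 2.3 and 4.3 still promise it.

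**Working it through.** The plan gives no expected dose, spread or power for this endpoint, so there is no figure to reproduce. The check counts steroid-days inside each window, with prescribing held identical in both arms and only the symptom stop date differing.

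Inputs:

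- Symptom duration D: 13 or 9 days. These are background medians in protocol 7.1, for standard of care and for standard of care plus long-term macrolides. They are not estimates for BCT197.
- Days from symptom start to first study dose, l: 1, 3 or 5, one value from each level of the SAP 8.6.2.1 factor, "time from start of current COPD exacerbation to first IMP dosing (≤2 days, 3-4 days or ≥5 days".
- Steroid start: the calendar day before first study dose. Protocol 9.1.1 and exclusion criterion 2 allow treatment of the current exacerbation to begin at most 24 hours before randomisation.
- Course length C: 5, 10 or 14 days, assumed.
- Daily dose: constant, assumed. It cancels from the percentages.

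Count the first-dose day as Day 1. A symptom period of D days, both ends included, ends on Day D − l. The course covers the day before Day 1 through Day C − 1. Therefore:

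- symptom-window count = min(C, D − l + 1)
- fixed Day 1 to 14 count = C − 1, whatever D is

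With D = 13 the cap D − l + 1 is 13, 11 and 9 for l = 1, 3 and 5. With D = 9 it is 9, 7 and 5.

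| l (days) | C (days) | Count, D = 13 | Count, D = 9 | Fall | Fixed Day 1–14, both arms |
|---|---|---|---|---|---|
| 1 | 5 | 5 | 5 | 0% | 4 |
| 1 | 10 | 10 | 9 | 1/10 = 10% | 9 |
| 1 | 14 | 13 | 9 | 4/13 = 31% | 13 |
| 3 | 5 | 5 | 5 | 0% | 4 |
| 3 | 10 | 10 | 7 | 3/10 = 30% | 9 |
| 3 | 14 | 11 | 7 | 4/11 = 36% | 13 |
| 5 | 5 | 5 | 5 | 0% | 4 |
| 5 | 10 | 9 | 5 | 4/9 = 44% | 9 |
| 5 | 14 | 9 | 5 | 4/9 = 44% | 13 |

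Take l = 3 and C = 10 as an example. The course runs to Day 9, but the 9-day symptom period ends on Day 6. Days 7, 8 and 9 are taken and not counted.

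Pre-dose steroid is one counted day in every row. In the shorter-symptom arm that is between 1/9 = 11% and 1/5 = 20% of the total. It is settled before randomisation and should balance across arms, so it adds noise and not bias.

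For the undefined cases, SAP 7.1.4.16 closes the period only at the symptom stop date and gives no alternative. SAP 7.2.2.2 leaves a stop date with a missing month as missing, which also leaves the period without an end.

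**The case against.** The strongest reply is that the SAP openly changed the question. If the interest is the steroid needed to control this exacerbation, then start to stop is the natural period, and a shorter exacerbation that uses less steroid is part of the benefit. That stands as a reason to report the total. It does not make it a substitute for the listed endpoint: it omits the tail of any course that outlasts symptoms, so it cannot separate less prescribing from a shorter count.

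It is also fair that a 5-day course, a length protocol 9.2 discusses, shows no effect. Later steroid use is not lost entirely either: treatment-failure criterion 3, the counts of steroid-treated exacerbations and the Stabilisation Phase medication tables all touch on it, though none gives a dose.

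Some stronger readings are tempting, and the documents do not support them:

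- *Early death or withdrawal looks like steroid sparing because of the new window.* The SAP has no truncation rule, so such a period is undefined and not short. If both windows were cut at withdrawal, leaving on Day 4 instead of Day 14 would lose 10 days of steroid in the fixed window (14 − 4) and 10 in the symptom window with one pre-dose day (15 − 5).
- *Several days of pre-dose steroid are counted, back to symptom onset.* The 24-hour eligibility limit prevents this for the current exacerbation.
- *The test is chosen after unblinded inspection.* SAP 8.6.4.3 says that "the skewness and kurtosis measurements will be considered as supportive indicators", but not when or on what grouping they are examined.
- *The past tense in SAP 9 means the window was chosen after results were seen.* No timing is given, and SAP 3.2.3 keeps analysts blinded until database lock.

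**Conclusion.** The concern holds in a limited form. The symptom window makes the counting period depend on a post-randomisation date that treatment can change. From window length alone, the apparent saving ranges from 0% to 44% in the illustration. That range rests on the assumed course lengths, the constant dose, the onset leads and a 4-day difference in symptom duration; none of these is a trial result. The artefact needs the drug to change symptom duration. If it does not, the windows are comparable between arms and this route creates no false difference.

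Separately, and without any assumption, SAP 2.3 and 4.3 disagree with 7.1.4.16 and 8.6.4.3, the Day 14 to Week 26 dose goes unanalysed, and unresolved symptoms have no rule. The consequences are modest: the endpoint is exploratory, the change is disclosed, and protocol 13.5.1 treats all analyses as exploratory.

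**What to change.** - Analyse both protocol windows as the listed exploratory endpoint: first study dose to Day 14, and Day 14 to Week 26. State which window takes Day 14 itself. Report time observed for patients who die or withdraw early.
- Keep the symptom-window total as a supplementary analysis that answers the question in SAP 9, with a stated rule for symptoms that have not stopped by death, withdrawal or end of study.
- Align SAP 2.3 and 4.3 with 7.1.4.16 and 8.6.4.3, and revise the entry in SAP 9 to match.

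The cost is SAP wording and one extra table. The medication form and the prednisone conversion are unchanged. The SAP's indication filter already covers exacerbations during the study, so only the date limits differ.
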